##### *Hypotheses:*

1. **PCMH** is more effective than **FFS** in reducing weight at 24 months.
2. **DM** is more effective than **FFS** in reducing weight at 24 months.
3. **DM** is more effective than **PCMH** in reducing weight at 24 months.
- 4a. **PCMH** is more effective than **FFS** at improving patient-centered outcomes, including blood pressure, laboratory measures (fasting glucose and lipids), quality of life, sleep, and stress.
- 4b. **DM** is more effective than **FFS** at improving patient-centered outcomes, including blood pressure, laboratory measures (fasting glucose and lipids), quality of life, sleep, and stress.
5. **DM** and **PCMH** will show larger effects over **FFS** for those with lower education, lower income, who travel longer distances to receive care, and who are employed full-time.
6. Aim 6 includes exploratory qualitative and quantitative process measures with no explicit hypotheses.

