## C. Sample Size, Statistical Methods, and Power Calculation

### C1. Analytic and statistical methods (including randomization)

**Randomization.** Thirty-six primary care practices from the rural Midwestern U.S. will be randomly allocated in equal proportions (1:1:1) to each of the three arms (FFS, PCMH, DM). Randomization will be stratified by institutional affiliation (KUMC, UNMC, Marshfield Clinic) within three cohorts.

**Missing data.** Based on our prior history using a similar retention plan in the rural setting, we expect to retain a minimum of 80% of participants (with a goal of 90%) at 24 months across all three treatment arms. We will document reasons for loss to follow-up. Participants who are removed from study for pregnancy, bariatric surgery, medical safety reasons, behavioral problems, or death will be excluded from analyses. All primary analyses will be conducted using intent-to-treat. We will evaluate the missing data pattern for differential loss to follow-up based upon treatment arm. All of the covariates (other than the outcomes) will be collected at baseline, and with our data quality controls we don't expect this data to be missing. In the absence of differential loss to follow-up, missing weight data will be treated as missing at random and addressed using maximum likelihood methods.

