### **Secondary aim 4: patient-centered outcomes**

Each patient-centered outcome at 24 months (and all relevant intermediate study visits) will be compared across all treatment arms using separate hierarchical linear mixed models.

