## **E2e. Outcome measures**

Outcome measures have been selected with input from our Patient Advisory Board and are supported by the literature. See Table 5 for the list of measures and estimated time to complete. The goal will be to complete the assessment visits within a -7 days/+21 day window of the target date. We will allow for a 3 month window for 6 and 18 month visits if an assessment visit appointment needs to be rescheduled and a 4 month window for the 24 month visit if an assessment visit appointment needs to be rescheduled. Chart review may be used to capture medications and number of clinic visits as well as missing weight data.

**Anthropomorphic measures.** Weight, and blood pressure will be directly measured and recorded at baseline, 6, 18, and 24 months during in-clinic assessment visits. Height will be measured at baseline only. These measures will be collected by clinic staff. Participants will be weighed in light clothing (shorts and t-shirt) in a fasting state using a calibrated digital scale accurate to 0.1 kg. Height will be measured with a stadiometer to calculate BMI. Blood pressure will be measured by clinic staff after the patient rests in a seated position for 5 minutes. Two measurements will be taken and recorded. If either the systolic or diastolic measurements are greater than 5mm Hg apart, a third measurement will be taken after a one-minute break. Estimated time for in-person assessment visit procedures is 15-20 minutes. If a patient is unable to come to the clinic for the data collection visit, an in-home visit or a visit at another location convenient for the patient, may be conducted.

**Fasting glucose and lipids.** A clinic phlebotomist or nurse will collect blood samples required for analysis of fasting glucose and lipids, to include LDL, HDL, triglycerides, and total cholesterol. Laboratory results

will be sent to the PCP per the laboratory and practice's standard operating procedures. The practice will in turn provide the results to KUMC study personnel (see section E1 for specifics).

**Questionnaires.** Self-report questionnaires will be administered via on-line REDCap surveys sent by email or by hard copy surveys sent via regular mail, depending on patient preference. Patients will be asked to complete questionnaires at all five time points (baseline, 6, 12, 18, and 24 month visits). Patients must complete the baseline questionnaires prior to enrolling in the trial (see section C1).

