**Demographic information.** Information will be collected at baseline on date of birth, race, ethnicity, income, marital status, level of education, employment status, time off work for study counseling visits, physical address, insurance status and type, and years living in rural area. Updates will occur at 12 and 24 months.

**Medical history.** Self-reported medical history, including smoking and weight loss history will be collected at baseline. At each follow-up questionnaire, patients will be asked to report hospitalizations/serious adverse events, exercise-related injuries/illnesses, and changes to smoking status. Any serious adverse events reported by patients via the self-reported medical history will be followed up on by KUMC study personnel (see Section I6).

**Medication Information.** Baseline medications will be collected through a phone interview after the patient has signed the baseline survey consent (see Section III C1). Changes in medications will be self-reported at 6mo, 12mo, 18mo, and 24mo.

**SF-12** (general quality of life) is a 12-item survey that measures physical and mental health-related quality of life. The SF-12 is a shortened version of the original SF-36, which has been established as a reliable and valid measure of quality of life and has been widely used, however has been insensitive to quality of life based on BMI and weight change over time. The SF-12 has been shown to detect differences in quality of life among overweight and obese individuals when compared to normal weight controls.

**Impact of Weight on Quality of Life-Lite (IWQOL-L)** is a 31-item self-report measure specifically designed to measure the effects of weight on quality of life that is an abbreviated version of an original 74-item IWQOL measure. The IWQOL-L assesses five domains of functioning: physical function, self-esteem, sexual life, public distress, and work and responses are measured on a 5 point Likert scale from "never true" to "always true." The measure yields a total score and five subscale scores. For overweight/obese samples, the IWQOL-L has demonstrated reliability and internal consistency, construct validity, and discriminant validity when compared to other quality of life measures, detects quality of life changes in response to weight loss during an intervention, and distinguishes differences in quality of life based on BMI.

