### **E3. Research Purposes/Standard Care**

The four in-clinic assessment visits and the accompanying lab work will not be billable to patients or their insurance companies. In the fee-for-service arm, the practice may elect to bill Medicare for the counseling sessions for patients with Medicare coverage. There is no patient co-pay for this provision. In addition,

participants will likely be visiting their PCP more frequently than usual for study-related visits. As a result, the PCP may request to see their patients more regularly to deliver standard medical care for other co-morbid conditions (i.e. hypertension or diabetes). All standard medical care will be billed to the participant's insurance in the usual way. The participant will be responsible for any co-pays or deductibles according to their insurance coverage.

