## F. Risk Benefit Assessment

### F1. Physical risks to participants

**Exercise.** Risks in this study are primarily related to exercise, an intervention component in all three study arms. Moderate intensity physical activity has few serious risks especially for those with clearance from a medical provider. Physical activity may cause temporary discomfort associated with exertion, muscle soreness, or musculoskeletal injuries. Accidents with physical activity, such as falls or sprained ankles, are also possible. In the DPP study, the occurrence of musculoskeletal injuries was 3% higher in the lifestyle intervention compared to the placebo control arm. Some risk for cardiovascular complications exist for participants with cardiovascular risk factors (e.g., history of MI, hypertension, diabetes). Maximum risk estimates of major cardiovascular events during strenuous exercise are 0.6 to 6.0 events per 10,000 person-hours for women and 0.3 to 2.7 events per 10,000 person-hours for men. However, exercise of all levels is beneficial for reducing cardiac events overall (both at rest and during exercise).

**Diet.** The dietary recommendation for all three study arms is  $\geq 1,200$  kcal/day and therefore avoids the risks associated with very low calorie diets. Although not common in this type of program or this level of caloric intake, calorie restriction can lead to inadequate nutrition or rapid weight loss. Rapid weight loss (>3 lbs per week for several weeks) typically associated with very low calorie diets, unlike the one used in this intervention, may lead to gallstones. Some patients with diabetes may be susceptible to hypoglycemia. Weight loss also has the potential to increase risk of hypotension for patients who are using medications that lower blood pressure.

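### Aim 4 compares blood pressure, glucose and lipids across arms without using the medication changes the trial collects, so a null or a positive difference could be misread

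*Combined protocol and SAP*

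**What the plan says.** Hypotheses 4a and 4b (section I.A2) claim that PCMH and DM are each more effective than FFS at "improving patient-centered outcomes, including blood pressure, laboratory measures (fasting glucose and lipids), quality of life, sleep, and stress". The Aim 4 analysis in section II.C1 is one sentence: each outcome, at 24 months and at the relevant intermediate visits, "will be compared across all treatment arms using separate hierarchical linear mixed models".

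Medication data are gathered. Section II.E2e states "Baseline medications will be collected through a phone interview" and "Changes in medications will be self-reported at 6mo, 12mo, 18mo, and 24mo", and Table 5 shows the same schedule. A second source is optional: "Chart review may be used to capture medications and number of clinic visits as well as missing weight data".

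Nothing in II.C1 uses the follow-up medication data. On covariates it says "All of the covariates (other than the outcomes) will be collected at baseline". The sensitivity step for potential confounders adjusts only for baseline variables that turn out to differ across arms. Intent-to-treat is stated for the primary analyses only.

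On care during the trial, section II.E3 says that, because of extra study visits, "the PCP may request to see their patients more regularly to deliver standard medical care for other co-morbid conditions". Sections II.F4 and III.E repeat this. Section II.F1 says "Weight loss also has the potential to increase risk of hypotension for patients who are using medications that lower blood pressure", and adds that some patients with diabetes may be prone to hypoglycemia.

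**The concern.** Blood pressure, glucose and lipids respond to drugs as well as to weight. Hypertension and diabetes are not exclusions (II.D2), so treated patients will enrol, and their PCPs keep control of that treatment for two years.

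If treatment changes differ by arm, the measured values mix the effect of the lifestyle programme with the effect of the drugs. A null result could mean no benefit, or equal control on less medication. A positive result could mean better control through weight loss, or simply more drug treatment in that arm. These readings lead to different conclusions about 4a and 4b. The plan as written cannot tell them apart, although the data to help do so are collected.

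**Working it through.** **1. Is follow-up medication used anywhere?** The II.C1 text for aims 1 to 6, the missing-data paragraph and the confounder paragraph contain no term for it. Baseline medication could enter the confounder step if imbalanced. Changes after baseline cannot. The clause allowing the analysis to be adapted sits under aims 1 to 3 and does not mention medication.

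**2. Could treatment differ by arm?** Scheduled in-clinic counseling sessions, from Table 1 and II.E2c:
- FFS: 4 (month 1) + 10 (months 2 to 6) + 18 (months 7 to 24) = 32, with the PCP delivering them or on hand.
- PCMH: at least 12 (months 1 to 3) + 2 (month 4) = 14, led by a counselor.
- DM: 0; all 12 + 6 + 18 = 36 sessions are by phone.

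Three routes follow, and they do not all point the same way:
- More practice contact could raise treatment in FFS.
- If PCMH and DM produce more weight loss, as V.B expects, hypotension or hypoglycemia could lead to drug reduction there.
- DM sends the PCP progress reports after 3 months and around 6, 12, 18 and 24 months, with recommendations for action and ad hoc reports for critical events (II.E2c). New or worsening symptoms heard in DM sessions are referred to the PCP (II.K3). This could raise or lower treatment in DM.

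Laboratory results go to the PCP in every arm (II.F1), so they do not by themselves separate the arms.

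**3. The plan's own power figure.** Section II.C3 gives power for weight only: 80% for 2.75 kg, SD 8, ICC 0.05, 12 practices of 40 per arm, alpha 0.025.
- Design effect = 1 + (40 − 1) × 0.05 = 2.95; effective n per arm = 480 / 2.95 = 162.7.
- Standard error = 8 × √(2 / 162.7) = 0.887 kg; two-sided power = 0.805. The stated 80% reproduces.

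No SD, effect size or power is given for any Aim 4 outcome.

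**4. Possible size, on assumed inputs.** The documents give no medication rate or drug effect. Shift = arm difference in net intensification (started or increased minus stopped or reduced) × drug effect.
- Systolic pressure: 0.10 × 5 = 0.5 mmHg to 0.20 × 10 = 2.0 mmHg.
- Glucose: 0.05 × 15 = 0.75 mg/dL to 0.10 × 30 = 3.0 mg/dL.

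**5. Effect on a comparison, also assumed.** Take a drug-free systolic difference of 5 mmHg, SD 15, ICC 0.05, two-sided alpha 0.05 and 32 completers per practice (80% of 40). Effective n per arm = 384 / (1 + 31 × 0.05) = 384 / 2.55 = 150.6; standard error = 15 × √(2 / 150.6) = 1.73 mmHg.

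| Excess net intensification in FFS | Expected difference | Power |
|---|---|---|
| 0 points | 5.0 mmHg | 0.82 |
| 10 points | 4.5 to 4.0 mmHg | 0.74 to 0.64 |
| 20 points | 4.0 to 3.0 mmHg | 0.64 to 0.41 |

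With no excess, an SD of 12 to 18 gives power of 0.95 to 0.67. If the excess of 10 to 20 points lies in PCMH or DM instead, the difference grows to between 5 + 0.5 = 5.5 and 5 + 2.0 = 7.0 mmHg.

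**The case against.** The strongest reply is that this is a pragmatic comparison of care models, which keeps some differences between arms on purpose (II.I4). If a model leads PCPs to treat more, that is part of its effect, and the measured-value comparison estimates it correctly. This stands, and the comparison should be kept. But the plan does not state this target for Aim 4, and even under it a reader needs medication by arm to know how a difference arose.

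A reader might go further and infer that the protocol expects PCP treatment to depend on arm, that a real benefit of PCMH or DM would be masked, and that 4a and 4b would be wrongly rejected. The documents do not support this:
- The sentences on extra PCP care name no arm and speak only of what may happen.
- FFS sessions may be given by auxiliary staff, and the protocol expects attendance to differ across arms (III.C4), so 32 scheduled sessions are not 32 PCP encounters.
- Section II.F1 names risks; it does not say that drugs will be reduced.
- Reports and referrals from DM could increase treatment there and exaggerate its benefit.
- Hypotheses 4a and 4b concern improvement in the measures, not equal control on fewer drugs.
- A shift of at most 2.0 mmHg, on the assumed inputs, removes or reverses a difference only if that difference is about 2 mmHg or less.

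**Conclusion.** The gap is real and of moderate importance. Medication changes are collected at every follow-up and used in no Aim 4 analysis, and the baseline-only sensitivity step cannot stand in for them. That treatment could differ by arm is a reasonable inference from the design, not a statement in the protocol. Direction and size are open. The figures of 0.5 to 2.0 mmHg and 0.75 to 3.0 mg/dL, and the fall in power from 0.82 to between 0.74 and 0.41, rest wholly on assumed inputs and show only that the effect could matter. The consequence is that a null or positive result on these outcomes could be misread, not that the planned comparison is invalid. The primary weight comparison and its power are unaffected.

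**What to change.** In the Aim 4 section of II.C1, for blood pressure, fasting glucose and lipids:

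1. Keep the measured-value comparison and state that it targets the effect of the care model regardless of medication changes.
2. Add baseline use of the relevant drug class (antihypertensive, glucose-lowering or lipid-lowering) as a covariate.
3. Compare drugs started or increased, and drugs stopped or reduced, by class and arm at 6 and 24 months, and at 18 months as well for blood pressure. Use chart review where available to check self-report.
4. Pre-specify one supportive analysis. An example is to add a range of constants to the values of patients whose drugs were started or increased and subtract them where drugs were stopped or reduced, with the sign reversed for HDL. Interpret 4a and 4b for these outcomes alongside it. Other methods would also serve; what matters is choosing one in advance.

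Do not enter post-baseline medication as a covariate: it can itself be affected by arm, so adjusting for it could introduce bias.

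The cost is coding of data already collected, plus one supportive analysis for each of three outcome families. Self-reported changes may lack dose detail, so increases and reductions may be less complete than starts and stops; the report should say so.

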### **Secondary aim 5: assess heterogeneity of treatment effects (HTE) across participants**

We anticipate treatment effects will vary across participants based on characteristics identified by the literature and by our patient partners as important for service utilization. Specifically, we hypothesize that DM and PCMH will show larger effects over FFS for racial/ethnic minorities (compared to White non-Hispanic), those with lower education (less than Bachelors degree), and those with lower income (e.g., less than \$50K household income). This is because the more intensive treatment in DM and PCMH may be especially important for subgroups who have fewer resources and face greater life stress, as is often the case for rural minorities in a predominantly White rural Midwestern region. We also hypothesize that DM and PCMH will show larger effects over FFS for participants who travel longer distances/have longer travel time to receive care or who are employed full-time because the traditional face-to-face office visit during regular clinic hours may limit their uptake of treatment. We will also explore interactions between treatment conditions and weight loss history (particularly any history of seeking assistance for weight loss) as participants with prior knowledge and skills for successful weight loss may benefit more from the brief counseling provided in FFS. Using separate hierarchical linear mixed models predicting weight loss over 24 months, we will examine interactions between each participant factor and treatment arms.

### **Secondary aim 6: evaluate the reach and sustainability of the interventions with the RE-AIM framework (Reach, Adoption, Implementation, Maintenance)**

Adoption within KUMC-affiliated sites will be evaluated by comparing practice characteristics across participating and non-participating practices (that were contacted about the study) using two sample comparisons (chi square or t-tests). After aggregating to the practice level, patient-level factors for reach (e.g., participation rates) and implementation (e.g., session attendance, ratings of care) will be tested and compared across arms using separate analysis of variance (ANOVA) models. Maintenance of weight loss services at the practice-level will be reported as simple frequencies.

**Potential confounders:** For all statistical models, sensitivity analyses will be performed using the models above but also adjusting for potential confounders among the baseline variables identified as varying across arms based on their standardized differences.

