### **C3. Power calculation and sample size**

A total of 36 practices with 40 participants per practice will be enrolled in the study (1440 participants total). Twelve practices (480 participants total) will be enrolled in each arm (FFS, PCMH, DM). A net treatment effect of 2.75 kg is supported by the available literature and our previous work. Treatment effects for PCP counseling alone with varying levels of intervention intensity have ranged from 0.1 to 1.7 kg at 12 to 24 months follow-up with the majority falling below 1 kg. For this pragmatic trial conducted in underserved rural areas, we expect the FFS treatment effect to fall in the lower end of this range. Team-based care approaches with obesity counseling delivered by auxiliary staff (PCMH) have ranged from 2.9 to 5.1 kg at 24 mo. In an entirely remote disease management program, Appel et al. reported weight loss of 4.6 kg at 24 mo. Our remote group phone-based program currently being delivered outside the primary care setting has shown 10.2 kg loss at 18 mo in preliminary analyses. We expect this to be lower in a pragmatic primary care trial, however a net effect  $\geq 2.75$  kg is achievable. To determine sample size, we set the type I error at 0.025 (overall type I error rate of 0.05 for first two aims), intraclass correlation coefficient at 0.05, and 40 patients/clinic. With 36 clinics, the trial will have 80% power to detect a net treatment effect of 2.75 kg (SD = 8).

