### **E2f. Process measures**

We will use the RE-AIM framework to evaluate Reach (at the patient level), Adoption (at the practice level), Implementation (at patient and practice level), and Maintenance (at the practice level). Table 6 describes quantitative RE-AIM measures. To inform and augment our quantitative RE-AIM implementation measures, we will also conduct a qualitative process evaluation.

Table 6. RE-AIM Measures

Reach (representativeness of participants)
 
 
• % of patients in registries who respond to recruitment mailings
 
• % of patients in clinic registries who enroll
 
• Comparison of demographics and co-morbidities between enrolled participants at the ten Marshfield clinic sites and all patients on the original study registries at the Marshfield clinic sites, given their ability to query their common EMR.
 
• Comparison of demographics between enrolled patients and patients on mailing lists who do not enroll (all sites)
 

Effectiveness (impact at participant level)
 
 
• measured with patient-centered outcomes (Aims 1-5)
 

Adoption (representativeness of practices)
 
Comparison between participating and non-participating practices within KUMC network on characteristics such as the following:
 
 
• practice type (e.g., FQHC, hospital-owned, stand-alone)
 
• practices and systems to address counseling for diet, physical activity, and weight management (for participating sites only).
 
• presence of registered dietitians or behavioral counselors
 
• degree of rurality as this corresponds to access to other community resources
 
• distance to a large hospital as this is associated with scope of practice in the rural setting
 

Implementation (process by which interventions are delivered)
 
 
• Counseling session attendance
 
• Provider completion of trainings
 
• Provider self-assessed competencies
 
• Provider-reported barriers to implementation (survey measure, qualitative interviews)
 
• Patient satisfaction and experience of care (survey measure, qualitative interviews)
 

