#### E5. Timeline (Figure 3)

The original funding period for this study was 5 years, January 1, 2015 to December 31, 2019. A global contract modification fully executed in February 2018 extended the period of performance through April 30, 2020. The final timeline is included in Figure 3. All project milestones, as required by PCORI, will be completed within this time frame. The study will be implemented in three cohorts, with 12 primary care practices in each cohort (4 in each of the 3 arms). Patient recruitment will begin in January 2016 for cohort 1, June 2016 for cohort 2 and September 2016 for cohort 3. Practices in the PCMH and DM arms will enroll 40 patients over a 6 month time period. The FFS arm will enroll 40 patients over a 9 month period (indicated in the timeline below with dotted lines). Each patient in all arms will be followed for 2 years. Analysis and dissemination of the primary outcomes will happen in the final 6 months of the project period.

Figure 3. Study Timeline

	Year 1 - 2015				Year 2 - 2016				Year 3 - 2017				Year 4 - 2018				Year 5 - 2019				Year 6 - 2020	
	Q1	Q2	Q3	Q4	Q1	Q2	Q3	Q4	Q1	Q2	Q3	Q4	Q1	Q2	Q3	Q4	Q1	Q2	Q3	Q4	Q1	Q2
Cohort 1	Study Preparation IRB Approval Practice Recruitment DSMB Charter Obesity Trainings			Practice Training	Recruitment		Phase 1		Phase 2										Analysis and Dissemination			
Cohort 2					Practice Training	Recruitment		Phase 1		Phase 2												
Cohort 3						Practice Training	Recruitment		Phase 1		Phase 2											

Figure 4. Study Flow

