Recruitment will also occur through in-clinic approaches. Study brochures will be distributed at various places in the clinics (passive approach), and providers will be able to directly refer patients during routine medical visits (active approach). Study brochures will contain a link to our RE-POWER website containing basic study information. The website will be contained within the KUMC system and is being developed with the help of KUMC Information Technology personnel. Clinic staff will instruct interested patients to contact the central recruitment and screening line. If practices have difficulty attaining their stated goal of 40 patients, additional recruitment efforts may be utilized to identify patients. Examples of these additional avenues include the use of press releases/news briefs in local newspapers, on practice websites and Facebook pages; placement of referral posters in the local community, and/or welcoming existing study participants to refer their acquaintances who go to the same clinic by sharing the study line.

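### Aim 6: the percentage of registry patients who enrol cannot reliably be read as reach when arms are compared, because all practices share a goal of 40 and FFS has 9 months against 6

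*Combined protocol and SAP*

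**What the plan says.** Section II.C1 (Secondary aim 6) states: "patient-level factors for reach (e.g., participation rates) and implementation (e.g., session attendance, ratings of care) will be tested and compared across arms". The tests are ANOVA models, one per factor, fitted to data aggregated by practice.

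Table 6 (II.E2f) lists four reach measures. Two are rates: the percentage "of patients in registries who respond to recruitment mailings" and the percentage "of patients in clinic registries who enroll". The other two compare the characteristics of enrolled patients with those of the registry or of patients who did not enrol.

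The recruitment goal is the same everywhere: 36 practices, 40 participants each, 12 practices and 480 participants per arm (II.C3). The time allowed differs. Section II.E5 says "Practices in the PCMH and DM arms will enroll 40 patients over a 6 month time period", but "The FFS arm will enroll 40 patients over a 9 month period". Section III.A1-2 adds: "If practices have difficulty attaining their stated goal of 40 patients, additional recruitment efforts may be utilized to identify patients". Section V.B treats 40 as a mean per practice. No hard cap is stated, and nothing says whether practices go on enrolling beyond 40.

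Section II.I3 asks each practice for a registry of roughly 300 to 400 patients. No section adjusts the reach comparison for recruitment time or for the common goal. Section I.A2 describes Aim 6 as exploratory, without hypotheses.

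**The concern.** Percent enrolled is the enrolled count divided by registry size. The count is steered towards one goal in all arms, and the time allowed to reach it differs by arm. An ANOVA on this percentage may therefore describe the recruitment plan rather than the appeal of the care model.

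The distortion can go either way. A model that attracts patients faster may look no better than the others, or FFS may look better only because it recruited for longer. Reach of the three arms is a stated secondary aim, so a formal test with this property could lead to a wrong statement about which model rural patients take up.

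The sensitivity analysis for potential confounders in II.C1 does not help. It adjusts for baseline variables. Window length is not one of them, and because it is fixed by arm it cannot be separated from FFS by covariate adjustment.

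**Working it through.** **The plan's own figure.** The documents give no power for the reach comparison. The goal of 40 belongs to the primary power calculation (II.C3), which reproduces:

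- Design effect = 1 + (40 − 1) × 0.05 = 2.95.
- Effective n per arm = 480 / 2.95 = 162.7.
- SE = 8 × √(2 / 162.7) = 0.887 kg, and 2.75 / 0.887 = 3.10.
- With two-sided alpha 0.025 (critical value 2.24), power = 0.805, against 80% stated.

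So 40 per practice is a sample-size quota for the weight analysis.

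**If every practice meets its goal and stops.** Percent enrolled = 40 / registry size: 40/400 = 10.0% and 40/300 = 13.3%, in any arm. Filling the full windows means 40/9 = 4.4 enrolments per month in FFS and 40/6 = 6.7 in PCMH and DM. Percent enrolled shows these as equal.

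**If goals are missed.** Let u be the monthly uptake as a share of the registry, assumed constant. Percent enrolled is about 9u in FFS and 6u in the other arms.

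- Equal uptake, u = 1.25%: 9 × 1.25 = 11.25% in FFS against 6 × 1.25 = 7.5%, a ratio of 1.5 from the window alone.
- FFS uptake one third lower, 1.0% against 1.5%: 9 × 1.0 = 9.0% and 6 × 1.5 = 9.0%. The deficit vanishes.

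**Simulation of the planned ANOVA.** There were 12 practices per arm, alpha 0.05 and 3,000 replicates. Registry size was drawn uniformly from 300 to 400. Counts were Poisson, with a gamma practice effect (CV 0.25) and constant monthly uptake. Apart from the approximate registry size and the number of practices, these are assumptions. Entries are mean percent enrolled (FFS / PCMH / DM) and the rejection rate.

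| Monthly uptake, % (FFS / PCMH / DM) | 9/6/6 months, stop at 40 | 9/6/6 months, no stop | 6/6/6 months, no stop |
|---|---|---|---|
| 3.0 / 4.5 / 6.0 | 11.5 / 11.5 / 11.5; 5% | 27.1 / 27.0 / 36.0; 76% | 18.0 / 27.1 / 35.9; 100% |
| 1.25 in all | 10.0 / 7.4 / 7.4; 85% | 11.2 / 7.5 / 7.5; 91% | 7.5 in all; 5% |
| 1.0 / 1.5 / 1.5 | 8.6 in all; 5% | 9.0 in all; 5% | 6.0 / 9.0 / 9.0; 85% |
| 0.5 / 2.5 / 2.5 | 4.5 / 11.1 / 11.1; 100% | 4.5 / 15.0 / 15.0; 100% | 3.0 / 15.0 / 15.0; 100% |
| 1.0 / 1.0 / 2.5 | 8.6 / 6.0 / 11.1; 100% | 9.0 / 6.0 / 15.0; 100% | 6.0 / 6.0 / 15.0; 100% |

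Row 1 shows masking by the common goal. Rows 2 and 3 show the window creating an FFS advantage and hiding an FFS deficit, with or without a stop at 40. Row 4 shows that a large FFS shortfall is still detected. In row 5, DM is correctly above PCMH, but FFS is falsely above PCMH.

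**Check on the obvious remedy.** Counting only the first 6 months looks fair. But if FFS recruits evenly over its planned 9 months, it has 40 × 6/9 = 26.7 patients at month 6. That is 26.7/400 = 6.7% to 26.7/300 = 8.9%, against 10.0% to 13.3% in the other arms: one third lower simply because FFS kept to its schedule.

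**The case against.** A reader might infer that the Aim 6 test cannot show any difference in reach, because the design fixes the numerator. The documents do not support that:

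- The 40 is a goal and a mean without a stated cap, and extra recruitment is only permitted when a practice lags. Shortfalls can occur and carry information.
- PCMH and DM have equal windows, so their comparison is free of the window problem. It is affected only by the common goal, when both arms meet it.
- The window favours FFS, so lower FFS enrolment despite the longer window would still be interpretable.
- Mailing response and the two representativeness comparisons are not set by the quota.

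A reader might also infer that FFS was given 9 months because patient demand was expected to be lower. The documents give no reason for it; practice capacity for individual visits would explain it equally well. The 4.4 and 6.7 per month are therefore planned paces, not evidence of demand.

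Two further worries are weak. Off-registry recruits do not inflate the measure as worded, because the Table 6 numerator is already limited to registry patients. Registry size differs across randomised arms only by chance: with the quota binding, the simulated rejection rate stays near the nominal 5%.

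Finally, Aim 6 is exploratory, and access is also examined through the Aim 5 interactions and session attendance. This limits the consequence. It does not make percent enrolled interpretable as reach in a formal comparison involving FFS, or in any comparison where the goals are met.

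**Conclusion.** The concern holds for one measure. Percent of registry patients enrolled is not a reliable cross-arm measure of reach. If goals are met and recruitment stops there, it sits at about 10.0% to 13.3% in every arm, and even a two-fold true difference is rejected only about 5% of the time. If goals are missed, the 1.5-fold longer window favours FFS: 85% false rejection at equal uptake of 1.25% per month, and 5% rejection where FFS uptake is truly one third lower (85% with equal windows).

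The rejection rates depend on the assumed uptake, its variation between practices and a stop at 40. The 10.0% to 13.3% depends on the approximate registry requirement. The direction of the window effect depends on neither the registry size nor the stop.

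The point does not extend to the other Table 6 reach measures, to large shortfalls, or to the primary weight analysis and its power. It is a modest point about an exploratory aim, worth acting on because the correction is cheap.

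**What to change.** In the Aim 6 analysis and Table 6:

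1. Do not test total enrolment over registry size across arms as the reach measure. Report it descriptively by arm, with recruitment duration and route.
2. Base the cross-arm reach comparison on two measures not set by the quota or the window: response to the first mailing within the same fixed number of weeks in all arms, and acceptance among patients screened as eligible. Section II.D1 already has eligible patients who cannot attend their arm's visits recorded as declining, with the reason, but no analysis of these records is planned.
3. Read the two together. Recruitment materials are the same at all sites (II.I4), so mailing response may be insensitive to arm. Acceptance is closer to the visit format actually offered.
4. Enrolment in a common first 6 months, or per registry patient-month until the goal is met, may be shown as supportive only. State that the planned slower FFS schedule can itself lower it.
5. Keep registry patients who enrolled through a poster or referral in the numerator; they were reached.

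The cost is wording and a little more analysis of recruitment data already tracked centrally (II.I2). Total percent enrolled is no longer formally tested across arms. All FFS enrolments, including those in months 7 to 9, stay in the outcome analyses.
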